The following screening assessments will be administered via Qualtrics or REDCap, web-based data collection platforms hosted by the University of Minnesota's CTSI:

- 1) Demographic History Questionnaire, which will assess age, gender, ethnicity, race, education, income, marital status, living situation, and employment history.
- 2) Center for Epidemiological Studies-Depression Scale (CES-D; Radloff, 1977), which measures symptoms of depression
- 3) Contemplation Ladder (Abrams, et al., 2003) to assess intention to quit smoking.

In the event that the Qualtrics/REDCap websites are not functioning, the assessments will be printed out and administered on paper. The source documents will be kept in the participant's binder. The interviewer will enter the data into Qualtrics/REDCap when it resumes functioning properly. This information should be recorded in the 'End of Visit Evaluation Form' and entered in to REDCap.

Eligibility Determination

Research staff will determine initial eligibility after reviewing all eligibility criteria except for the medical/psychiatric history. Researchers will pay ineligible participants \$35 for their time spent completing the screening assessments. The LMP will not review the medical history forms of participants who are not eligible for other, non-medical reasons.

If the participant is deemed eligible, then she/he will provide saliva and urine samples, complete the Baseline assessments, and be scheduled for Lab Session 1. They will receive \$70 for completing both the Screening and Baseline procedures. Participants will be instructed to use tobacco products as they normally would between the Screening/Baseline visit and the night before Lab Session 1; participants should not use any tobacco products on the day of Lab Session 1.

Final eligibility of the participant will be determined by a licensed medical professional (LMP) after reviewing the Brief Medical History Questionnaire, Medical History Follow-Up Questionnaire and the MINI suicide subscale. If the participant's score on the CESD indicates elevated symptoms of depression, then the CESD will be submitted to the LMP for review as well. The LMP will sign off prior to Lab Session 1 that the participant is medically stable to use the study product(s). If the LMP determines a participant is not medically stable enough to continue in the study, then the researcher will contact the participant prior to Lab Session 1 to cancel the lab visit.

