- 5) Vaping device: Vaping devices can expose users to several harmful chemicals, including nicotine. Nicotine, which is also in cigarettes, may lead to some of the same diseases as smoking. Exactly what other chemicals are in vaping devices, and how they might be harmful, is not completely understood. Vaping device aerosol is not harmless "water vapor", although it is generally contains fewer toxic chemicals than cigarettes. The most common side effects related to vaping are changes in taste, mucus in throat/sinus, dry mouth, dry cough, throat irritation, sore throat, mouth ulcers, dizziness, headache, and nausea. On rare occasions, batteries from vaping devices have exploded and injured users. However, this is extremely unlikely to happen in this study. The U.S. Centers for Disease Control and Prevention (CDC) and the Food and Drug Administration (FDA) are investigating recent reports of serious lung disease associated with the use of vaping/e-cigarette devices. Many of the illnesses are related to vaping cannabis oil. FDA has advised people to avoid buying vaping products on the street, to refrain from vaping THC oil, and warned against modifying or adding any substance to products purchased at stores. If you use a vaping device/e-cigarette products, you should watch for symptoms such as cough, shortness of breath, chest pain, nausea, vomiting, diarrhea, abdominal pain, fatigue, fever, and weight loss, and get medical attention right away for any health concerns. You can also call your local poison control center at [name]."
- 6) Nicotine is an addictive chemical. All products containing nicotine can become addictive and lead to longer-term use in the future. Exposure to smoke and nicotine in this project is carefully supervised and limited, so that it is not substantially more than what the participant is exposed to on a daily basis. Only those teenagers who are daily cigarettes smokers will be allowed to participate. Symptoms of too much nicotine include headache, dizziness, shakiness, nausea, vomiting or diarrhea, weakness, and fast heartbeat. You will be observed for any of these side effects and if they occur, we may stop the session.

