The following assessments will be administered as an interview and entered into REDCap by the interviewer:

- 1) Concomitant Medications Form
- 2) Health Changes Questionnaire
- 3) Adverse Event Form, if applicable
- 4) TLFB Questionnaire

PRE-TASK assessments will be administered using Qualtrics or REDCap:

- 1) MNWS
- 2) QSU-10 Usual Brand Version
- 3) PANAS

Sampling Phase Procedures

In the *Sampling Phase* (35 min), participants will be oriented to task procedures and shown the products available for that session. In Lab Sessions 2 through 5, two products will be available: (a) cigarettes (NNC or VLNC) and (b) vaping devices containing e-liquids with the assigned nicotine concentration and flavor characteristics for that session. Participants will have selected their e-liquid flavors during Lab Session 1.

Once the task begins, all instructions will be delivered via computer; sessions will be continuously observed by a research assistant through a one-way mirror. Participants will be prompted via computerized instructions to take four timed puffs of the cigarette and then complete the Product Rating Forms. Following a 15-min delay to allow the effects of the cigarette to dissipate, participants will be prompted to take four timed puffs of the vaping device and then complete the Product Rating Forms, followed by another 15-min delay prior to the *Preference Phase*. During protocol breaks, participants will be allowed to watch TV or read magazines.

Product Rating Forms will be administered using Qualtrics or REDCap immediately after sampling the product:

- 1) MNWS
- 2) QSU-10 Usual Brand Version
- 3) PANAS
- 4) CES – Study Cigarette and Vaping Device Versions
- 5) PHRS – Study Cigarette and Vaping Device Versions
- 6) CPT – Study Cigarette and Vaping Device Versions

Preference Phase Procedures

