 - CO is greater than 50 ppm if CO at Screening/Baseline Visit is < 20 ppm.
 - CO is greater than 60 ppm if CO at Screening/Baseline Visit is 20 – 34 ppm.
 - CO is greater than 70 ppm if CO at Screening/Baseline Visit is 35 – 49 ppm.
- Blood Pressure:
 - The 'Adverse Event Form' and 'Blood Pressure and Heart Rate Symptom Checklist' should be completed if an automatic **and** subsequent manual blood pressure measurement during the same visit is **at or above 160/100**
 - The 'Adverse Event Form' and 'Blood Pressure and Heart Rate Symptom Checklist' should be completed if an automatic **and** subsequent manual blood pressure measurement during the same visit is **below 90/50 and the participant is experiencing symptoms** listed on the 'Blood Pressure and Heart Rate Symptom Checklist.'
- Heart Rate:
 - The 'Adverse Event Form' and 'Blood Pressure and Heart Rate Symptom Checklist' should be completed if an automatic **and** subsequent manual heart rate measurement during the same visit is **at or above 105 bpm.**

- The 'Adverse Event Form' and 'Blood Pressure and Heart Rate Symptom Checklist' should be completed if an automatic **and** subsequent manual heart rate measurement during the same visit is **below 45 bpm and the participant is experiencing symptoms** listed on the 'Blood Pressure and Heart Rate Symptom Checklist.'

Management of SAEs and Other Study Risks

The site medical professional will review all AEs. A study participant may be discontinued from the study if the medical professional and/or PI determine it is the best decision in order to protect the safety of a participant. In the event that a participant either withdraws from the study or the investigator decides to discontinue a participant due to an AE/SAE, the participant will have appropriate follow-up medical monitoring. The participant experiencing an AE/SAE will be followed until the problem resolves, stabilizes, or is clearly unrelated to the study cigarettes. Any AE that remains open will be reviewed and closed at the 30 day follow-up interview.

Reporting of SAEs to the IRB, FDA, and NIDA

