Serious adverse events (SAEs) as defined in 21 CFR 312.32 (death, life-threatening, hospitalization (initial or prolonged), disability or permanent damage, congenital anomaly/birth defect, required intervention to prevent permanent impairment or damage (devices), other serious (important medical outcomes)) that are related or possibly related to study participation will be reported to the Administrative Core, all site IRBs, the NIDA Scientific Officer, the NIDA Project Officer, FDA, and the Data Safety and Monitoring Board within 72 hours. All Site IRBs require that fatalities related to the study be reported within 24 hours, that all other SAEs be reported within 5 business days. Reports of all SAEs will also be documented within NIDA's SAE data monitoring system, or SAETRS, within 72 hours.

Reporting of IRB Actions to NIDA

Actions taken by the Brown University IRB in response to AEs/SAEs will be reported to NIDA in the annual noncompetitive continuation application, as will reports of changes or amendments to the protocol as a result of an AE/SAE. Recommendation for trial discontinuation, for significant changes or amendments to the protocol, or other significant findings as a result of an SAE will be reported immediately to the NIDA Scientific Officer and Project Officer by the Project PI.

Reporting Changes or Amendments to the Protocol

Any changes or amendments to the protocol made in response to adverse events/SAEs will be discussed with [name] and [name], and then requested in writing to the IRB, which will then grant or deny permission to make the requested change in protocol. Changes that significantly alter the scope of the research or the ability of the research to achieve its specific aims will be submitted to [name], the DSMB, FDA, and NIDA for approval prior to implementation. NIDA will be informed of any change that is significant enough for IRB review and changes the protocol in substantive ways (e.g., changes to procedures, recruitment strategy, inclusions/exclusion criteria), before such changes are implemented (except an urgent safety measure). Minor changes that do not alter the protocol in substantive ways (e.g., change in staff; new advertising venues) will not be reported to NIDA. Changes in protocol will also be documented in the noncompetitive continuation application.

Withdrawal or Monitoring of Participants

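### The rule for ending adverse event follow-up tests causality against the study cigarettes only, so it lets follow-up end on an unresolved event caused solely by the vaping device or e-liquid

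*Combined protocol and SAP*

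**What the plan says.** The follow-up rule stands in the protocol under Management of SAEs and Other Study Risks: "The participant experiencing an AE/SAE will be followed until the problem resolves, stabilizes, or is clearly unrelated to the study cigarettes". The same paragraph adds three provisions that do not depend on cause:

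- "The site medical professional will review all AEs".
- Participants who withdraw or are discontinued because of an AE or SAE receive medical monitoring afterwards.
- Any AE still open is reviewed and closed at the 30-day follow-up. The section on that call places it 25 to 35 days after Lab Session 5.

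The trial supplies two products. In Lab Session 1 participants practise with the vaping device and sample nicotine-free flavoured liquids. For Lab Sessions 2 to 5 the sampling procedures state: "two products will be available: (a) cigarettes (NNC or VLNC) and (b) vaping devices containing e-liquids with the assigned nicotine concentration".

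Potential risks of participation treats vaping separately from smoking (items 5 and 4). Item 5 says: "The most common side effects related to vaping are changes in taste, mucus in throat/sinus, dry mouth, dry cough, throat irritation". It also says: "On rare occasions, batteries from vaping devices have exploded and injured users". Exclusion criteria 12 and 13 remove people with known allergies to e-liquid constituents or previous adverse reactions to vaping.

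Reporting of SAEs to the IRB, FDA, and NIDA uses a wider reference than the follow-up rule. It covers serious events "that are related or possibly related to study participation will be reported to the Administrative Core" and other bodies. Eligibility Determination likewise refers to study products in general when the medical professional clears a participant.

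**The concern.** A causality test for ending follow-up should refer to everything the study gives the participant. Here it refers to one of two products. An event that the device or liquid alone has caused is study-related, yet it is also clearly unrelated to the cigarettes, so the wording allows it to be let go before it resolves or stabilises. The same serious event could be reportable under one section and released from follow-up under another.

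At stake are the care of the individual, in a sample aged 15 to 20, and the completeness of the Adverse Event Form for that event. The form is meant to record how long an event lasted and how it ended. The protocol's closing script tells participants that the risks of vaping are largely unknown.

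**Working it through.** The plan gives no figure to reproduce. The check is to apply the rule as written and then look for any other passage that would keep the event under follow-up.

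**Applying the rule.** Take events that have neither resolved nor stabilised, so that only the third condition is in play.

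| Event | Clearly unrelated to the study cigarettes? | May follow-up end? | If serious, reportable as related to study participation? |
|---|---|---|---|
| Battery injury from the device | Yes | Yes | Yes |
| Allergic reaction clearly due to the e-liquid | Yes | Yes | Yes |
| Cough, throat irritation or nausea after a session with both products | Rarely | Usually no | Yes, at least as possibly related |
| Event attributed to the study cigarette | No | No | Yes |

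The first two rows are the gap: reportable if serious, yet open to release while active. The third row shows its limit. In Sessions 2 to 5 the participant takes four study-cigarette puffs before vaping and may choose either product afterwards. In Session 1 cigarette puffs also come before the vaping practice. Shared symptoms therefore usually fail the word *clearly*.

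**Looking for a provision that closes the gap.**

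- Medical review covers every AE but sets no duration and does not alter the stop condition.
- Monitoring after withdrawal or discontinuation does not reach a participant who stays in the study.
- The 30-day step covers only AEs that are still open. An event already released under the third condition is not among them.
- The Health Changes Questionnaire is product-neutral and could pick up a worsening, but it asks about change since the last visit and does not reopen a released event.
- SAP section 6.6 defers recording to an Adverse Event SOP that is not in the documents.

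No passage extends the stop rule to the device or the liquid.

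**The period in which the wording can matter.** Apart from pregnancy, which stays open until delivery, open events are closed at the call. The difference is therefore confined to the time before it. For an event at Session 5 this is 25 to 35 days. For an event at Session 1, four further sessions at least 48 hours apart add 4 × 2 = 8 days, giving at least 8 + 25 = 33 days if all sessions are attended. There is no firm upper limit, because longer intervals can be approved.

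**The case against.** The strongest reply is that this is loose wording with little effect. Every AE is medically reviewed whatever its cause. Serious events are reported by relation to study participation. Any open AE, from either product, is closed at the 30-day call. Item 5 of the risk section calls a battery explosion extremely unlikely in this study, and people with known e-liquid allergies are excluded. Staff would probably read the rule sensibly, and the SOP may already be wider.

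Most of this stands, and it makes the point narrow. It does not change what the rule permits before the call, and a safety rule should not depend on its readers to correct it. If the SOP is wider, the SOP and protocol disagree and still need reconciling.

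A reader might infer more than the documents support:

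- *That the safety record would understate the seriousness of vaping events.* Seriousness follows the regulatory criteria cited in the protocol and not the length of follow-up. SAP section 6.6 tabulates AEs by cigarette group without formal testing. No comparison of vaping with cigarette events is planned, and both groups are scheduled for the same four e-cigarette conditions, so no trial contrast is shown to be biased.
- *That mouth ulcers, throat or lung symptoms fall through the gap.* With both products used in the same visit, these would rarely be clearly unrelated to the cigarettes.
- *That the amount of vaping measures the problem.* The number of puffs measures exposure and says nothing about how many events the wording affects.

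**Conclusion.** The point holds as a narrow error of scope in a safety rule. As written, the rule allows follow-up to end on an unresolved event that the vaping device or e-liquid alone has caused. It permits this and does not require it. All 120 planned participants are to receive the product that the rule omits, but the number of events affected cannot be derived from the documents and is likely to be very small. The effect is limited to the period before the 30-day call. SAE reporting, medical review and the efficacy analyses are untouched.

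The conclusion assumes that the three conditions are alternatives, as their wording indicates, and that the Adverse Event SOP, which could not be checked, does not already apply a wider test.

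**What to change.** Reconcile the causality reference under Management of SAEs and Other Study Risks with three other places: the vaping risks in Potential risks of participation, the two-product sampling procedures for Lab Sessions 2 to 5, and Reporting of SAEs to the IRB, FDA, and NIDA. The reference should cover all study products and study participation, not the cigarettes alone. Check that the Adverse Event SOP uses the same reference. The protocol's description of the Adverse Event Form lists no relatedness item, so the sponsor should also confirm where this judgement is recorded.

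The change concerns scope only. How events are managed medically, and the closure at the 30-day call, are left to the investigators. The cost is one phrase in the protocol, an SOP check, and a few more events kept open until they resolve, stabilise or reach the call. The SAP analyses need no change.

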Table of Contents

1.	3
2.	3
3.	3
3.1.	4
3.2.	4
4.	5
4.1.	5
4.2.	Per-protocol.....
	5
5.	5
5.1.	5
5.2.	5
5.3.	Error! Bookmark not defined.
5.4.	Safety Endpoints.....
	6
6.	6
6.1.	6
6.2.	6
6.3.	6
6.3.1.	6
6.3.2.	7
6.4.	7
6.5.	7
6.6.	8
6.7.	8
6.8.	8

1. Introduction

This document will serve as the Statistical Analysis Plan for CENIC 2 Project 3, entitled “Effects of Very Low Nicotine Content Cigarettes and E-cigarette Characteristics on Smoking in Adolescents. This document describes the planned statistical analysis for evaluating the effects of cigarette nicotine content, electronic cigarette (e-cig) nicotine concentration and e-cig flavor on combustible cigarette smoking in adolescents within a laboratory setting. Details for the proposed analysis of the primary and secondary endpoints are provided.

2. Trial Objectives

This study of adolescent smokers will examine the effects of cigarette nicotine content and e-cig availability, nicotine content and flavoring using a laboratory-based preference task in which the nicotine content of cigarettes, the concurrent availability of e-cigs, and the characteristics of e-cigs (nicotine concentration and flavors), are manipulated. The **primary aim** is to test the effects of nicotine content in cigarettes, and nicotine concentration and flavors in e-cigs on choices to smoke a combustible cigarette, vape an e-cig, or abstain from both, in a sample of adolescent smokers. The **secondary aim** will test the effects of nicotine content in cigarettes, nicotine concentration in e-cigs, and e-cig flavors on subjective effects. Lastly, the **exploratory aim** explores the extent to which participant factors (gender, CPD and dependence) influence the effects of nicotine content in cigarettes, nicotine concentration in e-cigs, and flavors in e-cigs.

3. Trial Design

This is a randomized, single site, double-blind, $2 \times 2 \times 2$ laboratory-based study conducted on 120 adolescent daily smokers. These smokers will be assigned to receive either normal nicotine content (NNC) or very low nicotine content (VLNC) cigarettes. The first laboratory session will be a control session with only cigarettes, and no e-cigs, available. This will be followed by the 4 e-cig laboratory sessions with cigarette (tobacco; tobacco menthol) flavored e-liquid or non-cigarette (e.g., fruit; mint; vanilla; candy) flavored e-liquid and two levels of nicotine concentration as shown in the table below.

NNC cigarettes: 5 sessions (n=60)			VLNC cigarettes: 5 sessions (n=60)		
	e-liquid flavors			e-liquid flavors	
e-liquid nic concentration	tobacco	non-tobacco	e-liquid nic concentration	tobacco	non-tobacco
3 mg/ml	x	x	3 mg/ml	x	x
18 mg/ml	x	x	18 mg/ml	x	x
No e-cig control	x		No e-cig control	x	

3.1. Randomization

Randomization will be done in two stages. In the first stage, each individual will be randomized in a 1:1 ratio to either the normal nicotine content (NNC) or the very low nicotine content (VLNC) cigarettes in a double blinded fashion. The randomization will be stratified by gender, menthol status and cigarettes per day (<9, 9+). The goal is 60 subjects per cigarette group. The second randomization stage will be done within the subjects. Individuals in the two cigarette groups will be assigned to all four combinations of sessions involving e-cigs (flavor and nicotine content each at 2 levels) in counter balanced order, which provides 24 possible orders for the four e-cig sessions. The no e-cig session will always be first followed by the e-cig sessions, in an order randomly chosen from one of the 24 possible orders without replacement. Once all 24 session orders have been exhausted, the process will start over with another set of 24 orders. Each cigarette group (n=60) will end up with the same arrangement of the four sessions occurring 2 to 3 times. This will not allow for the evaluation of an order effect in the data analysis, but it will prevent a systematic bias due to the arrangement of the sessions.

